**7.5.3.4. Strategy for covariates selection**

For multivariable Poisson models, the following strategy for covariates selection will be applied.

The model will include time-independent covariates at study entry from EPI-MAL-002.

The covariates are described in section [7.5.3.1](#).

Covariates occurring in less than 5% of the subjects (percentage will be computed over subjects both in 6-12 weeks and 5-17 months group) will not be included in the model. Of note, models will be run if a minimum number of cases of each endpoint are observed (at least 10 cases in total).

The predefined clinically relevant covariates described in section [7.5.3.2](#) will be forced into the models.

Covariates selection will be done using statistical significance. Confounders will be included in the multivariable models if univariate p-value will be less than 20%.

Co-linearity (i.e. correlation among predictor covariates) will be assessed on the full model including forced-in covariate and the other selected with the variance inflation factor (cutoff level = 10). The method is described in the following section [7.5.3.5](#).

Then the selected set of covariates will be entered in the final model without transformations and the full model will be presented.

**7.5.3.5. Method for assessing co-linearity****7.5.3.5.1. Fitting weights for generalised linear models**

The computation of the fitting weights will be conducted using the SAS GENMOD procedure.

For Poisson regression models the syntax will be:

```
PROC GENMOD data=<filename> ;
  CLASS X Z;
  MODEL Y= X Z / OFFSET=Ln_PY DIST=poisson LINK=log ;
  OUTPUT OUT=out HESSWT=W ;
  RUN;
```

#### **7.5.3.5.2. Assess variance inflation factor**

A weighted regression will be done with the complete set of covariates (including the forced-in covariates) using the weights computed at the previous step. This regression will be conducted using the SAS REG procedure, the option VIF gives the variance inflation factor:

```
PROC REG data=out ;
  WEIGHT W;
  MODEL Y= X Z / VIF ;
  RUN;
```

A variance inflation factor higher than 10 indicates a co-linearity issue regarding the concerned covariate. The decision to drop the covariate will be made on order of clinical importance.

#### **7.5.3.5.3. Variables transformation for the weighted regression**

Categorical covariates with at least 3 categories will be transformed into dummy variables to be used in the SAS REG procedure.

Example:

The covariate Z could take the 3 categories values: 1, 2 and 3.

3 dummy variables will be created:

```
Z1=1 if Z =1 else Z1=0;
Z2=1 if Z =2 else Z2=0;
Z3=1 if Z =3 else Z3=0;
```

If we choose the Z=1 as the reference category, the weighted regression will be:

```
PROC REG data=out ;
  WEIGHT W;
  MODEL Y= X Z2 Z3 / VIF ;
  RUN;
```

The choice of the reference category could have an influence on the variance inflation factor. It is recommended to choose the category with the larger fraction of the subjects.

Discrete variables and dichotomous variables will be left unchanged in the model.

## 8. CONDUCT OF ANALYSES

### 8.1. Sequence of analyses

Description	Analysis ID (SDD & CARS sub-folder)
First Progress Report	E1_02
....	E1_03
Interim analysis	E1_07
Final analysis	E1_01

### 8.2. Statistical considerations for interim analyses

#### 8.2.1. Selection of subjects

This interim analysis will be done with clean data\* collected on a sub-group of subjects from AS only having 6 months of follow-up following the administration of dose 3 of EPI vaccine (6-12 weeks group), or 6 months after Visit 3 (5-17 months group); corresponding to Visit 5.

No adjustment for controlling the alpha level was planned.

*\* Some data may change after the interim analysis as access to the eCRF will still be granted to sites and investigators throughout the follow-up period, until study conclusion.*

A cut-off date was defined as 5 October 2018.

The subjects from AS selected are those:

- with available Visit 5  $\leq$  5 October 2018
- with theoretical Visit 5  $\leq$  5 October 2018:
  - when Visit 5 is missing, a theoretical Visit 5 is computed based on ICF as
    - AS 6-12 Weeks or AS 5-17 catch-up:  
Inform consent date + 1 week + 8 months + 2weeks
    - AS 5-17 months 1st DTP:  
Inform consent date + 6 months + 8 months + 2weeks

Moreover, subjects from AS prematurely withdrawn (from any cause) before Visit 5 who should have had Visit 5 before the cut-off date are included in the interim analysis using the following rules:

- Visit 1 before 5 February 2018
- Visit 2 before 5 March 2018 if Visit 1 missing
- Visit 3 before 5 April 2018 if Visit 1 and Visit 2 missing
- Visit 4 before 20 May 2018 if Visit 1, Visit 2 and Visit 3 missing

- If all the above visits are missing
  - AS 6-12W or AS 5-17 catch-up: ICF before 5 February 2018
  - AS5-17 1st DTP: ICF before 5 February 2018 minus 6 months

It must be mentioned the last contact (see section [7.2.13](#)) applicable for the interim analysis should be <= Visit 5 or theoretical Visit 5.

Of note, the selection of the sub-group of subjects included in the interim analysis is done by the study-set up analyst.

### **8.2.2. Selection of endpoints**

The interim analysis will concern co-primary safety objectives and the main other secondary objectives (at 6 months post dose 3 of EPI vaccine for the purpose of this interim):

- To estimate the incidence of AESI, and of other AE leading to hospitalisation or death, in children, prior to implementation of RTS,S/AS01E.
- To estimate the incidence of aetiology confirmed meningitis, in children, prior to implementation of RTS,S/AS01E.
- To describe the causes of death, overall and by gender.
- To estimate the incidence of any malaria (including *P. falciparum* malaria) diagnosed by rapid diagnostic test (RDT) and/or microscopy.
- To estimate the incidence of severe malaria (including *P. falciparum* malaria) diagnosed by RDT and/or microscopy.
- To estimate the incidence of cerebral malaria (malaria diagnosed by RDT and/or microscopy).
- To estimate the mortality rate (all-cause mortality and deaths attributed to malaria (including *P. falciparum*), overall and by gender.

Description of surveillance quality indicator will also be part of the interim analysis.

A specific TFL dedicated to the Interim Analysis (IA) described all the analysis to be provided.

The following table summarises the analyses done by endpoint for the IA.

**Table 7 List of analyses by endpoints for IA**

EPI-MAL-002 : Summary of interim analysis			
	Description of events	Incidence following EPI vaccine or virtual vaccination After each dose, primary and secondary schedule	Incidence following: D3 → D3 + 6 Months
AESI:			
Suspected AESI			
AESI by case definition as listed in CRF	○	-	-
AESI grouped by body-system	○	-	-
Confirmed AESI according to PI (after 1st or 2nd line lab)			
AESI (by MedDRA SOC & PT)	○	-	-
AESI by case definition as listed in CRF	○	-	-
AESI grouped by body-system	○	-	-
Confirmed AESI according to final diagnosis Overall			
AESI (by MedDRA SOC & PT)	○	○	-
AESI by case definition as listed in CRF	○	○	-
AESI grouped by body-system	○	○	-
Confirmed AESI according to final diagnosis by level of certainty			
AESI by case definition as listed in CRF	○	○	-
Other AE leading to hospitalization or death			
According to PI diagnosis			
Other AE leading to hospitalisation or death (by MedDRA SOC & PT)	○	-	-
According to Expert diagnosis			
Other AE leading to hospitalisation or death (by MedDRA SOC & PT)	○	○	-
Meningitis			
According to PI (after 1st)			
Aetiology confirmed meningitis	○	-	-
Aetiology confirmed, and/or probable meningitis	○	-	-
Probable meningitis	○	-	-
Aetiology Confirmed and/or probable and/or suspected meningitis	○	-	-
According to PI (after 2nd)			
Aetiology confirmed meningitis	○	-	-
Aetiology confirmed, and/or probable meningitis	○	-	-
Probable meningitis	○	-	-
Aetiology Confirmed and/or probable and/or suspected meningitis	○	-	-
According to Final (Expert)			
Aetiology confirmed meningitis	○	○	-
Aetiology confirmed, and/or probable meningitis	○	○	-
Probable meningitis	○	○	-
Aetiology Confirmed and/or probable and/or suspected meningitis	○	○	-
Malaria			
According to PI diagnosis			
Any Malaria	○	-	-
P. falciparum Malaria	○	-	-
Severe Malaria	○	-	-
P. falciparum severe Malaria	○	-	-
Cerebral Malaria	○	-	-
According to Expert diagnosis			
Any Malaria	○	-	○
P. falciparum Malaria	○	-	○
Severe Malaria	○	-	○
P. falciparum severe Malaria	○	-	○
Cerebral Malaria	○	○	○
Death (overall and by gender)			
Death all cause	○	○	○
Death due to an AESI (all grouped)	○	○	○
Death due to another AE (all grouped)	○	○	○
Death due to meningitis	○	○	-
Death due to malaria (including P. falciparum malaria)	○	○	○
Death due to P. falciparum malaria	○	○	○
Surveillance indicator			
Foot positional deformations as a birth defect	○	-	-
Abscess at the injection site	○	○	-

## 9. CHANGES FROM PROTOCOL

- *Risk factors of other AE leading to hospitalisation or death will not be done by means of univariate and multivariable Poisson regressions as for AESI, meningitis and malaria.*

*Indeed, from a clinical point of view such models will not be relevant in the context of EPI-MAL-002. Those models will be done in the before-after comparison in EPI-MAL-003 study.*

*Descriptive analyses of risk factors will be done as planned.*

- *Aggregated variables recorded in EPI-MAL-005 study will be part of the analysis of EPI-MAL-003 study including comparison of EPI-MAL-002 and -003 data. Those aggregated variables will not be included as risk factors of malaria in EPI-MAL-002 study.*
- *Handling of missing data is not relevant in the context of EPI-MAL-002 study. Therefore, Section 9.7.8.1 of the protocol will not apply.*
- *Version 17 terminology of the statistical catalogue will be used for the final analysis leading to a minor impact: in the Study Report, “subject” will be replaced by “participant”. The adaptation is already done in the SAP/TFLs*

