9.7.8.1. Handling of missing data

A worst case allocation will be done for suspected events (i.e. suspected AESI, suspected malaria) for which confirmation of the outcome is not available. In such case a sensitivity analysis will be done considering these unresolved events as confirmed.

For the determinants included in multivariable models, a complete cases analysis will be performed as primary analysis (i.e. missing data will not be substituted).

As sensitivity analysis, for analysis of risk factors of the co-primary endpoint only, a precise diagnosis of missing pattern will be done to describe the kind of missing data (i.e. missing at random, missing completely at random and missing not at random).

Considering the diagnosis an appropriate method of imputation will be conducted and will only concern the covariates forced in the models. The strategy will be the following:

- For continuous covariates, a multiple imputation [[Rubin, 1987](#)] method will be applied to handle missing value if missing at random mechanism is confirmed. Indeed, as noted by Sterne et al [[Sterne, 2009](#)], multiple imputations may give misleading results in case data are missing not at random.

CONFIDENTIAL

115055 (EPI-MALARIA-002 VS AME)
Protocol Amendment 7 Final

- For categorical covariates, missing indicator method will be done (i.e. a specific category of missing value will be created).

Of note, if the “complete cases” analysis contains 90% of the subjects, no imputation will be done. In the case that for a single covariate more than 50% of values are missing, the covariate will not be included in the model.

The method of imputation will be detailed in the SAP.

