Detecting the occurrence of AESI, other AE leading to hospitalisation or death, and meningitis cases are the primary objectives of this study. AESI and meningitis cases require specific diagnostic methods and such data may not be routinely collected in the study settings, potentially leading to underreporting. Therefore, specific training and monitoring of the field teams (community health workers, health care facilities staff, physicians and hospital staff) will be provided. The reinforcement of the pharmacovigilance practices and clinical and laboratory data collection most close to routine medical practice is a key component of this study. All procedures will be performed in line with the current national guideline recommendations in each of the participating countries. Improvement in surveillance over time may increase sensitivity in detecting those events and this potential bias will be taken into account when analysing data collected over time. Surveillance quality indicators will be utilised to help detect trends in changes in surveillance capacity.

Longitudinal detection of events such as meningitis might also be difficult to interpret because of the changing meningitis disease epidemiology. The study will take place in countries of the “meningitis belt”, which is affected yearly by bacterial meningitis epidemics (mostly meningococcal meningitis). This zone comprises 22 countries from Senegal in the West to Ethiopia in the East. During 1993-2012, nearly one million suspected meningitis cases were reported; 80% of epidemics were caused by *Neisseria meningitidis* serogroup A. Despite successful introduction of a meningococcal A conjugate vaccine in the African meningitis belt since 2010 [Novak, 2012], meningococcal meningitis outbreaks may occur in some study sites during the EPI-MAL-002 study period, due to other *Neisseria meningitidis* serogroups, or if the study site is in a region/country which has not yet introduced the vaccine. Therefore, the interpretation of meningitis incidence rates should take into account the epidemiological context of each site. As for AESI, all efforts will be made to standardize meningitis diagnosis and reach an optimal proportion of laboratory confirmed cases to establish the aetiology. The case ascertainment process to classify meningitis cases will be based on additional laboratory testing (mainly based on molecular detection methods such as PCR) and the review of individual data by external experts.

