	
 
• Section 6.12: table 5 adapted
 
• Section 7.2.5: added category “No” or “negative” for specific subgroups
 
• Section 7.2.6: deletion of suspected AESI definition
 
• Section 7.2.7: addition of ICD-10 code related to febrile convulsion
 
• Section 7.2.12: final analysis will only include uncomplicated and severe malaria, including cerebral malaria, as per protocol
 
• Section 7.2.12: addition of process link to retrieve the categories of cause of death
 
• Section 7.2.14: addition of date of RTS,S for last contact date computation and clarification of last contact date
 
• Section 7.3: section handling missing data 
 
– Deletion of part related to missing covariates as not applicable for EPI-MAL-002as not applicable for EPI-MAL-002
 
– Addition of rules related to management of missed home visits to be consistent with EPI-MAL-003
 
 
 
• Section 7.5: 
 
– deletion of sections related to multilevel model, logistic regression and Cox model
 
– adaptation of covariates included in models; mainly deletion of variables from EPI-MAL-005
 
– deletion of models on hospitalised subjects only
 
– adaptation of Table 6
 
 
 
• Section 9: changes from protocol: 
 
Explaining deletion from analysis of: 
 
– Risk factors for other AEs leading to hospitalisation or death
 
– EPI-MAL-005 covariates consideration
 
– Handling of missing data
 
 
 
 
 
 
Amendment 2 text has been included in bold italics

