### **7.2.3. Date of occurrence**

The dates of occurrence of events are defined as follows depending on the endpoint:

- Suspected or confirmed AESI and meningitis reported at hospital:
  - Onset date of event
- Suspected AESI and suspected meningitis reported during outpatient visit (see section [7.3](#) for worst case allocation sensitivity analysis):
  - Admission date at outpatient visit
- Other AE leading to hospitalisation or death:
  - Onset date of event if AE is the primary diagnosis
  - Admission date at hospital otherwise
- Suspected or confirmed malaria cases:
  - Onset date of event for hospitalised cases
  - Admission date at outpatient visit otherwise
- Death:
  - Date of death reported in study conclusion

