### 7.3. Handling missing data

*For incidence rate computation, the missed visits will be considered as:*

- for the AS 5-17 months group*  
*If the three first home-visits planned according to the schedule are missing, the first home-visit will be imputed as:*
  - AS 5-17 months first DTP: Date of birth + 6 months*
  - AS 5-17 months catch-up: Date of ICF*
  - for the AS 6-12 weeks group: no imputation of missed visits as DTP vaccination dates will be considered for the computation of the follow-up.*

*Of note, the number of missed home-visits (without imputation) will be displayed on the flowchart section of the study report.*

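### SAP Amendment 2 drops the protocol's worst-case sensitivity analysis for unresolved suspected AESI and malaria, and the only reason given concerns missing covariates

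*SAP*

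**What the plan says.** Protocol 9.7.8.1 does two separate things. It first deals with outcomes: "A worst case allocation will be done for suspected events (i.e. suspected AESI, suspected malaria) for which confirmation of the outcome is not available", and "In such case a sensitivity analysis will be done considering these unresolved events as confirmed". It then gives rules for missing covariates in the multivariable models.

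SAP section 9 states "Handling of missing data is not relevant in the context of EPI-MAL-002 study" and concludes "Therefore, Section 9.7.8.1 of the protocol will not apply". That removes both parts. For the same amendment, the SAP document history describes the change to 7.3 as "Deletion of part related to missing covariates", plus new rules for missed home visits. The history separately records that the suspected-AESI definition was deleted from 7.2.6.

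SAP 7.2.3 still assigns an occurrence date to suspected AESI and suspected meningitis seen at outpatient visits, and refers to 7.3 "for worst case allocation sensitivity analysis". SAP 7.3 now opens "For incidence rate computation, the missed visits will be considered as" and contains only rules for missed home visits.

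On the case set, Protocol 9.7.5.2.1 groups AESI for confirmed and non-confirmed cases alike. SAP 6.9.2.1 and 6.9.3.1 restrict the final analysis to confirmed cases, and SAP 7.2.9 restricts malaria to cases meeting the protocol definition.

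**The concern.** EPI-MAL-002 exists to supply background rates for EPI-MAL-003. A rate built on confirmed cases depends partly on how often a suspected case can be confirmed. The protocol's worst-case analysis was the planned way of showing how much that matters for AESI and malaria. It has been withdrawn under a reason that does not address unresolved outcomes. A programmer following 7.2.3 will find nothing to implement, and a reader of the final report will not be able to tell a rate that is robust to case status from one that is not.

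**Working it through.** **Comparing the texts**

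| Item | Protocol | SAP Amendment 2 |
|---|---|---|
| Unresolved suspected AESI | Counted as confirmed in a sensitivity analysis (9.7.8.1) | Switched off (9); definition deleted (history, 7.2.6) |
| Unresolved suspected malaria | Same (9.7.8.1) | Switched off (9); final analysis per protocol definition only (7.2.9) |
| Suspected meningitis | Not named in the 9.7.8.1 rule | Rate kept for aetiology-confirmed, probable and/or clinically suspected cases (6.10.2.2, Table 5); outpatient-only suspected cases point to an empty place (7.2.3 to 7.3) |
| AESI case set | Confirmed and non-confirmed (9.7.5.2.1) | Confirmed only; noted in the history but not listed in section 9 |
| Reason given | – | Covariates only (history, 7.3); a general statement of irrelevance (9) |

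The worst-case orderings in SAP 7.2.8.1 and 7.2.8.2 decide which label survives when repeat visits are merged into one episode. They do not count unresolved events as confirmed, so they do not replace the dropped analysis. The interim plan (SAP Table 7) describes suspected AESI but plans no incidence for them. SAP 7.3 itself handles missing data, in the form of missed visits, which sits badly with the statement that the subject is not relevant.

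**Reproducing the plan's own precision figure**

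Inputs from Protocol 9.5: 10,000 children per group; follow-up censored at one month after doses 1 and 2; the full 6-week window after doses 3 and 4.

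- Person-years = 10,000 × (2/12 + 2 × 6/52) = 3,974.36, as in Table 6.
- Rate for x events = x / 3,974.36 × 100,000.
- Exact Poisson limits on the count: lower = χ²(0.025; 2x)/2, upper = χ²(0.975; 2x + 2)/2, each divided by person-years.
- For x = 1: 25.2 [0.6, 140.2] per 100,000 person-years, which matches the protocol. All rows of Tables 6 and 7 reproduce, so no numerical error is involved.

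**Illustration**

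The documents do not say how many events will be unresolved. Assume 1 confirmed event in the 6-week window and u unresolved events, with person-years held fixed:

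| u | Rate per 100,000 PY [95% limits] |
|---|---|
| 0 | 25.2 [0.6, 140.2] |
| 1 | 50.3 [6.1, 181.8] |
| 2 | 75.5 [15.6, 220.6] |
| 4 | 125.8 [40.8, 293.6] |
| 5 | 151.0 [55.4, 328.6] |
| 10 | 276.8 [138.2, 495.2] |

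From u = 5 the worst-case rate lies above the confirmed-only upper limit of 140.2.

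For all children under 5, person-years = 11,500 × 5 × 2 = 115,000 (Table 7). With 25 confirmed events: 21.7 [14.1, 32.1]; with 5 unresolved added, 26.1 [17.6, 37.2]; with 10, 30.4 [21.2, 42.3]; with 25, 43.5 [32.3, 57.3]. Here 10 unresolved events stay inside the confirmed-only interval and 25 do not. Protocol 9.5 gives no precision table for malaria, so none is attempted.

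**The case against.** Several points on the other side stand.

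- **Meningitis.** A reader might infer that meningitis also loses its wider estimate. It does not. The protocol rule does not name it, and SAP 6.10.2.2 keeps a rate that includes clinically suspected cases, among them those with no CSF sample and no alternative diagnosis. Only suspected meningitis seen solely at an outpatient visit is left without handling.
- **Upper bound.** A reader might say the rates now have no upper bound. Exact Poisson upper limits remain. What is missing is an estimate of sensitivity to case status, which those limits do not provide.
- **Breadth of confirmed cases.** Confirmed AESI means any AESI with an ICD-10 code other than not confirmed, and the investigator's diagnosis is used when there is no expert one (SAP 6.9.2.1). Any and severe malaria draw on outpatient visits as well as hospitalisations (SAP Table 4), and access to testing is to be ensured (Protocol 9.2.7.3.1). The unresolved group may be small, and a baseline biased low is plausible but not shown.
- **Under-reporting.** Protocol 9.9 warns that the required diagnostics may not be routine, "potentially leading to underreporting". That concerns events not detected or not diagnosed. Counting suspected events as confirmed cannot recover events that were never suspected, so the dropped analysis would not bound that limitation.
- **False vaccine signal.** A reader might infer that better confirmation in EPI-MAL-003 would appear as a vaccine effect with nothing to judge it against. The documents do not support that: Protocol 9.2 plans two exposed and two unexposed clusters per country, and 7.4 says events are monitored the same way in both studies.
- **Declared change.** SAP 9 does declare that 9.7.8.1 will not apply, and Protocol 9.7.4 allows changes that are described and justified in the final report. The earlier text of SAP 7.3 is not available, so its former content is inferred from the 7.2.3 pointer.

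None of this supplies a reason for dropping the outcome part, repairs the pointer, or gives the AESI and malaria rates a case-status sensitivity estimate.

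**Conclusion.** The point holds for AESI and malaria. The protocol's sensitivity analysis for unresolved suspected events is removed, the only specific justification concerns covariates, the reference from SAP 7.2.3 to 7.3 leads nowhere, and the confirmed-only AESI case set is not listed in SAP 9. The 7.2.3 pointer itself concerns AESI and meningitis, not malaria. For meningitis the gap is limited to cases suspected only at an outpatient visit.

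The primary confirmed-case estimates are not affected. The effect on interpretation depends on the number of unresolved events, which the documents do not give. At the counts used in Table 6, a handful would matter; if the number is near zero, the issue is one of documentation only. The illustration assumes that every unresolved event falls in the risk window, is the child's first countable event after that dose, and leaves person-years unchanged.

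**What to change.** 1. In SAP 9, limit the statement on missing data to the covariate part of Protocol 9.7.8.1.
2. In SAP 7.3, restore the sensitivity analysis that counts suspected AESI and suspected malaria as confirmed when they are unresolved, excluding those ruled out, and restore the suspected-AESI definition in 7.2.6.
3. Report the number of unresolved suspected cases by site and study group, and add one worst-case column to the AESI and malaria incidence tables.
4. State how suspected meningitis seen only at an outpatient visit is handled, so that the pointer in 7.2.3 resolves.
5. List the move to confirmed-only AESI in SAP 9 as a change from Protocol 9.7.5.2.1, with its reason.

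The cost is a few extra tables from data already collected. If the final analysis has already been run, label the addition post hoc. If the unresolved counts prove negligible, one sentence reporting them would close the point without the extra column.
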